In summary, evidence suggests that older adults can be educated and empowered to engage in discussions with their providers that result in favorable changes in their medication risk profile (including medications viewed as being difficult to discontinue, i.e., benzodiazepines). Prescriber-directed decision support can also improve the safety of medication regimens. Yet, there remains a need for a pragmatic model that simultaneously engages patients, pharmacists, and prescribers in the context of real-world, daily healthcare delivery to efficiently and safely reduce the use of CNS-active medications. Moreover, models that can sustain prescribing changes over time are paramount to achieve effects on health outcomes such as falls and fall-related injuries, as resumption of medications may otherwise occur.

In STOP-FALLS, we will adapt the EMPOWER patient-directed educational brochure together with the prescriber-directed decision support tool used in D-PRESCRIBE for use within the integrated healthcare delivery system at 9 KPWA clinics. If STOP-FALLS is successful, we expect it to significantly reduce the incidence of falls, fall-related injuries, and healthcare costs for injury care.

d. Data Analysis

Provide a brief description of the main data analysis plan.

Aim 2

Overview. Statistical analyses will be performed using statistical software (R, SAS, or STATA). Descriptive statistics will be computed and appropriate graphical summarizations (histograms, boxplots, scatterplots) will be made for all variables across the intervention clinics and usual care clinics to assess the comparability of the baseline characteristics and follow-up time of each group. Although we stratified our randomization on size and location of clinics and expect the KPWA population to stay relatively stable over the study time period, any patient characteristics which we find to be different (either clinically or statistically at P-value <0.10) between groups at baseline, known to be related to the outcome or likelihood of disenrollment from the health plan will be adjusted for in analyses. We will always include age, sex, and indicator of prior falls in the adjusted models. Statistical significance will be indicated by a P-value <0.05 and all tests and confidence intervals will be two-sided.

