Primary Outcome. To compare the primary outcome of reduction in number of medically treated falls between intervention and usual care groups over 12 to 24 months, we will run a Poisson regression model with indicator of intervention or usual care clinic and other adjustment variables. A participant's follow-up time within a clinic will start when they were sent a mailing (intervention group) or comparably for the usual care clinics we will mimic when they would have been sent a mailing if they were in the intervention group and start their follow-up time at that point. To account for differential follow-up time per participant we will include an offset term that is observed follow-up time and accounts for censoring due to disenrollment from the health plan (e.g., offset will be either to the end of the study period between 12-24 months depending on clinic and patient roll-out timing or time enrolled in the health plan over their clinics follow-up periods). To account for cluster randomization at the clinic level we will use generalized estimating equations (GEE) with a robust sandwich variance to account for clinic-level correlation. We will conduct similar models for 6- and 12-month follow-up times which are secondary time points. Further, to explore the timing of when the intervention effect may have occurred, we will run a Poisson model with three indicators of time periods (0-6 months (reference group), 6-12 months, 12-18 months, and 18-24 months) including interactions with time periods and indicator of intervention or usual care clinic. Each participant has up to 4 different outcome measures (less only if censored) in the model and the offset is determined by the time observed in a given time period. To account for multiple outcomes for a participant and cluster randomization we will apply Poisson regression with GEE and a robust sandwich variance.

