At clinic roll-out, the KPWHRI Study Programmer will access KPWA automated data (VDW tables) and receive data files from STRIPE, SMART and COMET to identify the eligible Intervention Group (see section 3.3 for eligibility criteria). The KPWHRI Programmer loads the sample into the study database. Every month, the KPWHRI programmer updates the medication lists for the Intervention Group and runs an algorithm to select which patients in the Intervention Group are mailed to that month (see Figure in section 7.1.e on the selection of who is mailed to each month). The KPWA survey research program will print notification letters and relevant patient brochures and mail these materials to patients. At the same time, the Research Specialist will send the Epic Staff Message, a message letting the provider know their patient was included in the study and a link to the EBPO of the same medication class. In order to ensure that KP providers are not confused by this communication, we will inform providers at the Intervention Clinics about this study and materials that they can expect to receive through morning huddles and/or brown bag lunches as deemed appropriate by the clinic managers.

One month after the initial brochure is sent, the KPWA survey research program will send out the postcard mailer.

The same process of identifying the sample will occur for usual care clinics at the time the matched intervention clinic goes live, but the Control Group and their respective providers will not receive any of the educational materials.

Providers:

Providers are not subjects in this research. We are not screening or recruiting providers for this study.

Prior to clinic rollout, the research team will explain the study to providers at team huddles and meetings (whichever individual clinics prefer) and the information to be shared at these huddles/meetings has been uploaded in IRBNet.

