6.5 Decisionally Impaired Subjects

Does this study involve consenting/assenting subject who may be unable to consent due to decisional impairment?

☐ YES ☒ NO

If YES, complete **Supplement F**.

7. Procedures – Primary Study Activities**7.1 Randomization, Interventions, and Clinical Procedures****a. Randomization**

Will subjects be randomized to receive procedures, activities, interventions, etc.?

☒ YES ☐ NO –

If YES, please describe the randomization.

This is applicable to PHASE II (Intervention) ONLY:

The unit of randomization is at the clinic level (stratified randomization by size and location of clinic), so individuals are not the unit of randomization. However, subjects are randomized to receive the intervention according to their assigned clinic. Of the 18 clinics identified for the trial, 9 clinics will be randomized to the intervention and 9 to usual care. The clinic pairs for the stratified randomization are as follows (approved by delivery system leaders):

Intervention Clinics	Control Clinics
Capitol Hill	Northgate
Veradale	Lidgerwood

Tacoma Medical	Steele St.
Burien	Renton
Bellevue	Redmond
Silverdale	Port Orchard
Lynnwood	Everett
Poulsbo	Federal way
Kent	Northshore

b. Clinical Trial

Is this study a clinical trial as defined by National Institutes of Health (NIH)?

NIH defines a clinical trial as "A research study in which one or more human subjects are prospectively assigned to one or more interventions (which may include placebo or other control) to evaluate the effects of those interventions on health-related biomedical or behavioral outcomes."

☒ **YES** ☐ **NO**

c. Study Interventions and/or Other Clinical Procedures

Does your study include any behavioral, educational or medical interventions, or any other clinical procedures (e.g., blood draw, blood pressure, training workshops)?

☒ **YES** ☐ **NO**

If YES, continue. If NO skip to 7.2

d. Summary of Intervention/Clinical Procedures

Please check boxes below and/or summarize intervention activities and/or other clinical procedures. Check all that apply.

☒ Educational/behavioral intervention (e.g., counseling program, clinical decision aid)

☐ Medical intervention (includes prescribing or administering drugs)

☐ Drug or medical device. IF CHECKED, complete **Supplement B**. Also contact IRB Office staff for required additional forms and information and check all boxes below that apply.

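### Clinics were randomised in nine pairs stratified by size and location, but the primary analysis ignores the pairs, so its standard error may be too wide or too narrow for the design

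*Combined protocol and SAP*

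**What the plan says.** **Design.** Section 7.1.a (Randomization) states: "The unit of randomization is at the clinic level (stratified randomization by size and location of clinic". It adds: "Of the 18 clinics identified for the trial, 9 clinics will be randomized to the intervention and 9 to usual care". It then gives a table of nine rows, each with one intervention and one control clinic, introduced by "The clinic pairs for the stratified randomization are as follows (approved by delivery system leaders". The same matching dates the control samples (Section 5.2.a): "The same process of identifying the sample will occur for usual care clinics at the time the matched intervention clinic goes live".

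**Analysis.** The overview in Section 2.2.d acknowledges the restriction: "Although we stratified our randomization on size and location of clinics". The covariates it goes on to name are all at patient level. One group is data-driven: "any patient characteristics which we find to be different (either clinically or statistically at P-value <0.10) between groups at baseline", together with characteristics related to the outcome or to disenrolment. The other is fixed: "We will always include age, sex, and indicator of prior falls in the adjusted models". The primary model follows: "we will run a Poisson regression model with indicator of intervention or usual care clinic and other adjustment variables". It is fitted by GEE with a robust sandwich variance for clinic-level correlation. Significance is two-sided at 0.05.

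No section puts pair, clinic size or location into the model or its variance. None names a reference distribution or a small-sample correction.

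**The concern.** Pairing restricts which allocations could have occurred. If paired clinics have similar fall rates, part of the between-clinic variation cancels in the comparison of arms. A clinic-level sandwich does not see this: it estimates the spread of clinics within each arm and so overstates the standard error. With only 18 clusters, between-clinic precision is the scarce resource.

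A second error works the other way. With nine clinics per arm, an uncorrected sandwich underestimates the variance. Which error dominates depends on how alike the paired clinics are, and the sponsor cannot know that when writing the plan. At stake is whether the primary interval and p-value have their stated coverage and error rate.

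**Working it through.** **Inputs from the documents.** 18 clinics in nine pairs, 9 per arm (Section 7.1.a); about 5000 participants (Section 3.1); follow-up of 12 to 24 months (Section 2.2.d); two-sided 0.05. The plan has no power calculation or precision figure to reproduce.

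**Assumptions.** 1.5 years of follow-up each; 0.1 to 0.2 medically treated falls per person-year; between-clinic CV 0.1 to 0.2; 0 to 70% of the between-clinic variance shared within pairs (the pair share).

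**Step 1: correlation of observed results within pairs.** With equal clinics, person-years per clinic are 5000 × 1.5 / 18 = 416.7. The Poisson variance of a clinic's log rate is 1 / (416.7 × rate), which is 0.024 at rate 0.1 and 0.012 at rate 0.2. The between-clinic variance is ln(1 + CV²), which is 0.00995 at CV 0.1 and 0.0392 at CV 0.2. The observed within-pair correlation is

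ρ = share × between-clinic variance / (between-clinic variance + Poisson variance).

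- Rate 0.1, CV 0.1: 0.00995 / 0.03395 = 0.29 at most; 0.15 at share 0.5; 0.21 at share 0.7.
- Rate 0.2, CV 0.2: 0.0392 / 0.0512 = 0.77 at most; 0.38 at share 0.5; 0.54 at share 0.7.

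**Step 2: reported against true standard error.** Let σ² be the variance of one clinic's log rate. The true variance of the log rate ratio is (2/9)σ²(1 − ρ). The uncorrected sandwich has expectation of about (8/9)(2/9)σ². So

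reported SE / true SE ≈ √[(8/9) / (1 − ρ)].

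This gives 0.94 at ρ = 0, 1.00 at ρ = 1/9 = 0.11, 1.06 at ρ = 0.21, and 1.38 at ρ = 0.54.

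**Step 3: simulation.** 40,000 replicates per scenario, 16 scenarios, clinic size CV 0.4 matched within pairs, no covariates. *Planned* is the Poisson GEE with clinic sandwich and a z reference, which is an assumption because the plan names none. *Unpaired t16* adds a 9/8 variance correction and t on 16 df. *Paired t8* is the mean of the nine pair log rate ratios with t on 8 df. Power is at an assumed rate ratio of 0.8.

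| Rate | CV | Pair share | Reported/true SE, planned | Type I, planned | Type I, paired t8 | Power, unpaired t16 | Power, paired t8 |
|---|---|---|---|---|---|---|---|
| 0.1 | 0.1 | 0 | 0.924 | 0.091 | 0.050 | 0.637 | 0.542 |
| 0.1 | 0.1 | 0.5 | 1.017 | 0.067 | 0.048 | 0.652 | 0.603 |
| 0.1 | 0.1 | 0.7 | 1.051 | 0.059 | 0.049 | 0.645 | 0.614 |
| 0.2 | 0.2 | 0 | 0.911 | 0.097 | 0.050 | 0.482 | 0.427 |
| 0.2 | 0.2 | 0.5 | 1.171 | 0.040 | 0.049 | 0.477 | 0.596 |
| 0.2 | 0.2 | 0.7 | 1.365 | 0.021 | 0.050 | 0.486 | 0.707 |

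Across all 16 scenarios, planned type I error ran from 0.021 to 0.097 and the paired t8 analysis from 0.048 to 0.050. A separate simulation with equal clinic sizes gave SE ratios of about 0.91 to 1.34 and planned type I error of 0.018 to 0.087. A within-pair permutation test stayed near 5% (0.044 to 0.048 in the null scenarios of a further run).

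**Step 4: price of pairing.** Critical values are 1.960 (z), 2.120 (t16) and 2.306 (t8). At ρ = 0 the paired interval is wider by 2.306/2.120 = 1.09 against a valid t16 interval, and by 2.306/1.960 = 1.18 against z. Break-even ρ is 1 − (2.120/2.306)² = 0.155 against t16, and 1 − (1.960/2.306)² = 0.28 against z, ignoring the sandwich bias. At pair share 0, the four rate and CV combinations lose about 5 to 10 points of power against unpaired t16, whose own type I error there was 0.056 to 0.059.

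**Step 5: permutation resolution.** With one independent draw per pair there are 2⁹ = 512 allocations, and the smallest two-sided p is 2/512 = 0.004.

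**The case against.** **The form asks only for a brief analysis summary.** The phrase about other adjustment variables is not expressly limited to patient characteristics, and the attached funding proposal is not visible here. This stands as a reason to ask for a statement. It does not supply a pair-aware analysis, because every covariate actually named is at patient level.

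**Analysing a paired design unpaired can be deliberate.** With nine pairs it can be defensible: omitting the pairs is by itself conservative, and the unpaired corrected analysis has more power in several of the scenarios, one of them at pair share 0.5. This stands. But the plan gives no such rationale and no small-sample correction, without which the unpaired choice is not safe either.

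**Stronger readings that the documents do not support.**

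- A reader might infer that leaving out the pairs biases the estimate or inflates false positives. Pairing protects the balance between arms. The inflation at low pair share comes from the uncorrected sandwich with 18 clusters.
- A reader might infer a definite gain, for example an interval factor of √0.5 × 2.306/2.120 = 0.77 at correlation 0.5. That uses a t16 comparator that the plan does not state, and a correlation of observed clinic results that Poisson noise dilutes. At rate 0.1 and CV 0.1 it cannot exceed 0.29.
- A reader might infer that pair must enter the model to carry calendar time. Matched go-live already balances launch dates across arms, and several clinics share a launch month (Section 2.3.c). Follow-up starts at each patient's actual or mimicked mailing, spread over up to 12 months within a clinic.

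**The allocation mechanism is not described.** Section 7.1.a gives strata and pairs but not how the draw was made, and Section 7.5 still refers to 8 intervention clinics. This stands and conditions the fix.

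**Conclusion.** The point holds as a mismatch between design and analysis that the sponsor should resolve before outcomes are analysed. The direction of the error is conditional: the reported standard error is too wide if pairs are prognostic and too narrow if they are not. Under the assumed ranges it is roughly 0.9 to 1.35 times the true value, with nominal 5% type I error between about 0.02 and 0.10. The plan does account for clustering by clinic; what is missing is the pair layer and a small-sample method. Because the documents give no fall rate, intraclass correlation or pair correlation, no fixed gain in precision can be claimed. The case for change rests on valid error rates across the whole range.

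**What to change.** Pre-specify a pair-respecting primary analysis:

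- **P-value:** a permutation test that swaps arms within the nine pairs. State how the allocation was drawn. The 512 allocations apply only if there was one independent draw per pair; otherwise permute over the allocations that could actually have occurred. Reconcile the count of intervention clinics in Section 7.5 with Section 7.1.a.
- **Interval:** from the same procedure by test inversion, or from the nine covariate-adjusted pair log rate ratios with t on 8 df.
- **Avoid:** simply adding pair indicators or clinic-level covariates to an uncorrected GEE, which risks a standard error that is too small.

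If the sponsor prefers to leave the pairs out, the plan should say why and name a small-sample correction and reference distribution.

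The cost is analysis wording only, with no new data. The downside, if the pairs prove uninformative, is an interval about 9% wider than a valid unpaired t16 interval and about 5 to 10 points of power in the simulated cases. Against an uncorrected z interval the widening is about 18%, part of which is that interval being too narrow.

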3.1 Study Population Tables

Provide the expected number of subjects for this study. **Complete this/these table(s) or use your own.** If there are multiple subject populations or multiple sub-studies, create separate tables for each population/site.

KPWA Population		
Population	Anticipated Number of subjects to be screened/invited	Anticipated Number of subjects to be enrolled
Focus Group Participants	400	40- enrollment complete
Cluster Randomized Trial Participants	5000	~5000
	Total: ~5040	Total: 5040

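### The primary GEE test on 18 clinics names no small-sample correction, reference distribution or handling of the clinic pairs, so its 5% error rate is not controlled

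*Combined protocol and SAP*

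**What the plan says.** The primary analysis is in section 2.2.d, Primary Outcome: "we will run a Poisson regression model with indicator of intervention or usual care clinic and other adjustment variables", with follow-up time as an offset. The clustering sentence is: "To account for cluster randomization at the clinic level we will use generalized estimating equations (GEE) with a robust sandwich variance". The 6- and 12-month analyses use similar models, and the period-by-arm model again uses GEE with a robust sandwich variance. The secondary overdose and crash-injury analyses are said to follow the primary one.

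The 2.2.d overview sets the error rate: "Statistical significance will be indicated by a P-value <0.05 and all tests and confidence intervals will be two-sided". It leaves the package open: "Statistical analyses will be performed using statistical software (R, SAS, or STATA"). On covariates it says: "We will always include age, sex, and indicator of prior falls in the adjusted models".

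Section 7.1.a gives the design: "Of the 18 clinics identified for the trial, 9 clinics will be randomized to the intervention and 9 to usual care". Randomization is stratified by clinic size and location, and a table of nine intervention-control pairs follows the words "The clinic pairs for the stratified randomization are as follows".

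No section mentions a bias-corrected variance, a t or F reference, a permutation test, or a pair or stratum term in the model.

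**The concern.** The sandwich variance is justified for a large number of clusters, and here there are nine per arm. Two errors then push the same way. The ordinary sandwich underestimates the variance of the arm contrast, and a normal reference ignores the uncertainty in that variance. Together they make P-values too small and intervals too short.

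The paired randomization can push the other way. If paired clinics resemble each other and the model ignores this, the variance is overstated.

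This is the test of the primary outcome, so the stated 5% carries the trial's main conclusion. Because the plan is silent and the software is open, the correction, and with it the P-value, could also be settled after the data are seen.

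**Working it through.** **The plan's own figure.** The documents give no power calculation, intracluster correlation, fall rate or clinic-size distribution. The only figure to test is the nominal two-sided 0.05 (z = 1.960).

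**Inputs from the documents.** 18 clinics, m = 9 per arm (section 7.1.a); about 5,000 participants (section 3.1); adjustment for age, sex and prior falls (section 2.2.d).

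**Step 1: equal clinics, no pair correlation.** Assume approximately normal clinic means. The ordinary sandwich equals (m-1)/m = 8/9 of the unbiased between-clinic variance. The correctly scaled statistic is t on 2m-2 = 16 df. So:

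- Type I error = P(|t16| > 1.960 × √(8/9)) = P(|t16| > 1.848) = 8.3%. This needs no intracluster correlation or fall rate.
- With the K/(K-1) = 18/17 variance factor and z: P(|t16| > 1.960 × √(8/9 × 18/17)) = P(|t16| > 1.901) = 7.5%.
- With the unbiased variance but still z: P(|t16| > 1.960) = 6.8%. Both parts of the correction are needed.
- Correct width relative to plain width: (2.120/1.960) × √(9/8) = 1.147. The plain interval is 1/1.147 = 87% of the correct one.

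Section 7.5 speaks of 8 intervention clinics, where sections 7.1.a and 7.1.e say 9; these must be reconciled. With 8 per arm the same formula gives P(|t14| > 1.960 × √(7/8)) = 8.8%.

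**Step 2: unequal clinics, covariates, no pair correlation.** Patient-level simulation under no effect: 5,000 patients, independence working correlation, adjustment for age, sex and prior falls, 6,000 trials per scenario (Monte Carlo SE about 0.4 points). Assumed, not in the documents: 0.1-0.3 falls per year, clinic SD on the log scale 0-0.30, coefficient of variation (CV) of clinic size 0-0.8, individual overdispersion.

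| Clinic sizes | Plain sandwich, z |
|---|---|
| Equal | 9.0% |
| CV 0.4, no clinic effect | 8.8% |
| CV 0.4, clinic effect | 9.2-9.9% |
| CV 0.6 | 10.3-11.1% |
| CV 0.8 | 10.8% |

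A separate check with CV up to 0.5 gave about 8.4-10.5%. In the patient-level simulation, Mancl-DeRouen with t on 16 df gave 3.9-4.9%. In a further unadjusted simulation with size CV up to 0.6, Kauermann-Carroll with t on 16 df gave 5.1-6.8%.

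**Step 3: pairs correlated, model ignores them.** If clinic means within a pair have correlation ρ, the variance of the contrast shrinks by (1-ρ), while the sandwich does not. The critical value becomes approximately 1.848/√(1-ρ):

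- ρ = 0.2: 1.848/√0.8 = 2.066, giving 5.5% (5.6% simulated).
- ρ = 0.5: 1.848/√0.5 = 2.613, giving 1.9% (2.1% simulated).
- Break-even: 1-ρ = (1.848/2.120)² = 0.76, so ρ is about 0.24.

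In patient-level data, sampling error dilutes a correlation between clinic effects, so the fall is smaller. The runs together gave about 6-8% at 0.2 and about 3-7% at 0.5. The documents give no value for this correlation.

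**Step 4: does t on 16 df alone settle it?** Not if pairing works. Without a pair term, Mancl-DeRouen with t on 16 df rejected 1.1-3.5% at correlations of 0.2-0.5, and Kauermann-Carroll 1.6-4.4%. That is lost power.

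**The case against.** There are four serious points on the other side.

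**The plan does not say the variance is uncorrected.** A bias-corrected sandwich is still a robust sandwich, and the text answers a form that asks for only a brief analysis description. This stands as to wording: the plain estimator is the ordinary reading, not a statement in the plan. The gap remains, because nothing fixes the correction or the reference distribution.

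**Pairing may cancel the inflation.** This is the main qualification, and it stands. A reader might infer that the false-positive rate is roughly twice nominal and that every interval is too narrow. The documents do not support that, because it assumes the nine pairs share none of the clinic variation. But the offset is neither planned nor quantified, and it can overshoot into a conservative test.

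**The top of the range may be too high.** Section 7.1.e gives monthly mailing caps of about 35-95 per clinic. If caps are proportional to clinic size, the size CV cannot exceed (95-35)/(2√(35 × 95)) = 0.52, so the 0.6 and 0.8 rows lie outside it. The section describes the 15% behind the cap both as a share of clinic visits and as a share of the clinic sample, so the bound is approximate. Within it, about 8.4-10.5% is the better range.

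**Other outcomes were not simulated.** Overdose, crash injury and the period-by-arm terms use the same approach, but the size of any error there is unknown. The interaction terms are partly within-clinic contrasts and may behave differently.

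**Conclusion.** The point holds as a failure to control the error rate, not as a demonstrated doubling of it. On the ordinary reading, the primary test has 8.3% type I error for equal clinics, given approximately normal clinic means and no pair correlation. With unequal clinics it is about 8-11% under the stated assumptions, if pairing explains little. It falls to about 6-8% at a within-pair correlation of 0.2 and about 3-7% at 0.5. The 87% interval width belongs to the equal-clinic, unpaired case. Since the documents give no pair correlation, fall rate or intracluster correlation, no single figure can be assigned to this trial.

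**What to change.** In section 2.2.d:

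1. Name one bias-corrected sandwich now, for example Kauermann-Carroll. In the equal-clinic, unpaired case it restores the unbiased variance exactly (factor 9/8). Mancl-DeRouen applies that factor twice and widens the interval by (9/8) × (2.120/1.960) = 1.217, more than the 1.147 needed there. With unequal sizes, however, Kauermann-Carroll was slightly liberal in simulation.
2. Use a t reference with cluster-based degrees of freedom: 18 - 2 = 16 for the unpaired analysis, fewer if pair or stratum terms are included. With all nine pairs in the model, 18 - 9 - 1 = 8.
3. State whether pairs or strata enter the model. Settle this together with item 2.
4. If allocation was within the nine listed pairs, add a permutation test over the 2^9 = 512 allocations as a sensitivity analysis. Its smallest two-sided P-value is 2/512 = 0.004, so it can reach 0.05.
5. Apply the same rules to the 6- and 12-month, period-by-arm and secondary clinic-clustered models.

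The cost is a few sentences, with no new data or design change. Intervals become about 15% wider in the equal-clinic, unpaired case. Pair terms cost degrees of freedom, and leaving them out costs power if the pairing is effective.
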